# **Brain Targets in Patients with Bladder Emptying Difficulties**

**NCT03574610**

**Document Date: January 24, 2020**

## Research Strategy: Supraspinal Targets in Neurogenic Voiding Dysfunction

### 1. SIGNIFICANCE

Voiding dysfunction (VD) is a morbid and costly urological condition characterized by intermittent, fluctuating, or absent flow of urine. VD may lead to incomplete bladder emptying or urinary retention, urinary tract infections, sepsis, bladder or kidney stones, and permanent renal failure and can be present in patients with or without neurologic disorders.

- *Currently the only available therapies for VD include indwelling bladder catheters or intermittent selfcatheterizations.*

Catheterization is a burden, in general, and even more so in neuropathic patients, in whom lower extremity spasms, compromised hand dexterity, or visual disturbances, may be present. The cost and morbid side effects (hematuria, pain, trauma, strictures, and infections), associated with catheterizations, urge us to look into alternate ***therapeutic targets for VD, possibly beyond the bladder, such as the brain*** (where bladder and urethral control centers are located).

The human lower urinary tract has two functions: storage and voiding. This study will concentrate on supraspinal (brain) areas controlling the delicate and complex neural circulatory (the “switch”) from storage of urine to initiation of voiding. Normal voluntary voiding is controlled by suprapontine centers in the brain, allowing the pontine micturition center to trigger (switch on) the voiding reflex. VD occurs if the detrusor muscle cannot maintain effective contractions (e.g., *detrusor underactivity*), if the urethra fails to relax and lower urethral resistance, or if there is failure in synchronizing these actions leading to detrusor sphincter dyssynergia (DSD) in subset of neuropathic patients. ***Almost all patients with DSD are dependent on catheterization and are at much higher risk for autonomic dysreflexia, recurrent urinary tract infections, and renal insufficiency.***

Animal models have conventionally been used to study neural control of the bladder. However, animals differ from humans in numerous ways (e.g. social behavior). Critical distinctions exist between voluntary voiding (humans) and more instinctive bladder emptying (animals), when all the social, emotional, and mechanical criteria for voiding are considered. ***The conscious human intention to void, or not to void, highlights the need for human research, rather than exclusive reliance on animal data, in brain control over bladder.***

With the evolution of neuroimaging tools and resources, such as functional magnetic resonance imaging (fMRI), we have begun to gain additional insight into brain control over bladder function in healthy individuals. ***Yet, our understanding of supraspinal centers and their role in initiating or modulating voiding continues to be rudimentary in patients with neurogenic*** (e.g. Multiple Sclerosis [MS] or Stroke) ***or nonneurogenic voiding dysfunction*** (e.g. underactive bladder or Fowler’s syndrome).

- The ***overall objective*** of my proposed study is to characterize and modulate specific supraspinal regions during the “switch over” of urine storage to voiding in MS patients with VD to improve voiding.
- Supraspinal involvement in VD in humans (especially in neuropathic patients) have not been investigated, and our proposed study will be the *seminal research* in the field.
- The findings from my proposed study may lay the foundation to study other etiologies of VD such as Underactive Bladder or detrusor underactivity, stroke, or Parkinson’s disease, all of significant interest to National Institute of Diabetes and Digestive and Kidney Diseases.

### 2. INNOVATION

Investigation of brain control over the bladder in healthy individuals through the use of functional neuroimaging shows that the initial afferent sensory input comes from the bladder during “bladder fullness or the strong desire to void”. Next, the forebrain determines the person’s social circumstances and whether to proceed with voiding

or not. Once it is socially acceptable to void, centers in the brain and spinal cord coordinate and initiate urethral sphincter/pelvic floor relaxation, followed by a sustained detrusor contraction. Specifically, the pontine micturition center (PMC) signals the bladder to begin the voiding phase when the sensations from the bladder are transmitted to the periaqueductal gray (PAG) and higher brain centers. Previous positron emission topography studies in *healthy* individuals have demonstrated activation of the right dorsomedial pontine tegmentum, PAG, hypothalamus, and the right inferior frontal gyrus at the time of voiding. **Neuroimaging may augment the diagnosis of VD and aid in therapeutic planning in certain etiologies of VD.**

- Combining urodynamic studies (UDS) with functional magnetic resonance imaging (fMRI) is technically challenging, but necessary, in order to elucidate simultaneous brain-bladder activities. We have established and refined our simultaneous platform in healthy individuals and neuropathic patients.
- Despite the challenges, our fMRI/UDS platform evaluates the entire bladder cycle, including the voiding phase. This is the strength and novelty of our protocol as, in contrast to other neuroimaging studies, individuals in our study void or attempt to void while in the MRI scanner during the UDS.
- In this proposal, we have taken **the next step to move beyond the exploratory phase** of identifying supraspinal targets involved in VD, into *targeted cortical stimulation of these regions (another testament to the novelty of our project)*.
- Our investigative brain targets will also include areas of **urethral activity**, which is innovative and not traditionally studied.

**Our fMRI/UDS platform:** UDS provides valuable information on bladder pressures and urethral sphincter function especially in patients with neurogenic VD. Over the past four years, we have established a concurrent fMRI/UDS platform in healthy controls and in MS patients and evaluated the entire bladder cycle in realtime in over fifty individuals, specifically *when patients void or attempt to void in the fMRI scanner while UDS is being performed. Our platform outperforms other neuroimaging studies, wherein voiding is not studied.*

[figure not shown]

[figure not shown]
Figure 1. A. Our concurrent UDS and fMRI set up where MRI-compatible bladder and rectal catheters are passed through a small opening in the wall between the control room and the scanner room (Philips Ingenia 3.0T full body scanner with a standard 12-channel head coil). B. Our combined fMRI and UDS testing protocol.

**Transcranial Magnetic Stimulation (TMS) and Transcranial Rotating Permanent Magnet Stimulator (TRPMS):** Currently, the only neuromodulation modalities available for bladder target the peripheral nerves, including the Sacral Neuromodulator, the Posterior Tibial Nerve Stimulator, and the intradetrusor injection of neurotoxin OnabotulinumtoxinA. Further, they mainly target the storage phase (urinary urgency and incontinence). **As part of my K12 proposal I have focused on identifying supraspinal changes following onabotulinumtoxinA injection in the bladder using our fMRI/UDS platform in MS patients.** While others have evaluated the brain changes following sacral neuromodulator use for overactive bladder patients.

- **However, to date, there has been no central (brain) neuromodulation for bladder and specifically for the voiding phase.** It has become prudent to look beyond the bladder in managing neurogenic bladder VD and fMRI/UDS identified supraspinal regions and our proposal offer some hope for potential therapeutic targets.

TMS is a non-invasive centrally acting electromagnetic neuromodulator that is held over the scalp and delivers a rapidly pulsed magnetic field to the cortex to activate neurons, within a limited area, without requiring anesthesia or causing any significant side effects. TMS and repetitive TMS (rTMS) are substantially safe and are widely used for brain mapping and/or to modulate cortical excitability. Two small studies have demonstrated the feasibility and efficacy of rTMS in patients with MS (n=10), and Parkinson's disease (n=8) with bladder symptoms. Their findings suggest that TMS improves both the storage and voiding phase, and reduces postvoid residuals of the urine, while appropriately increasing the detrusor pressure at the time of voiding. *Interestingly, in three MS patients with DSD, following rTMS, the abnormally high detrusor pressures at the time of voiding were decreased to a more appropriate level, possibly implying the restoration of synergistic voiding with coordinated relaxation of urethral sphincter and the pelvic floor.* In a more recent study, fifty-eight children (ages from 6 to 14) with nocturnal enuresis were randomly assigned to receive anticholinergic medication (oxybutynin), TMS, or placebo TMS. Authors reported improvements in bladder capacity, voiding scores, and enuresis events, seven months following TMS use.

**Limitations of TMS and Innovation in our proposal:** Commercialized TMS devices use large coils that restrict their portability and can only be applied to one location of the cortex. **However, brain control during voiding appears to be dependent on multiple regions and their connectivity including the urethral regions, requiring a transcranial modulator that could safely stimulate/inhibit multiple areas at the same time.** The neurophysiology and

neuromodulation laboratory at our institution has developed a non-invasive, portable, and *multifocal* brain magnetic modulator, called Transcranial Rotating Permanent Magnet Stimulator (TRPMS).

- TRPMS uses small, high field strength permanent magnets rapidly spun by miniature electric motors. It is therefore wearable and portable, and capable of multifocal stimulation. TRPMS will selectively **induce, modulate, or suppress** neuronal activity, and also **modulate the strengths of the functional connections between two or more cerebral cortical areas when they are stimulated simultaneously**, depending on the strength, frequency and pattern of stimulation.

Figure 2. TRPMS cap with microstimulators placed on sites corresponding to left primary motor, right lateral premotor, and right supplementary motor cortex. The smartphone image shows the Android app used to operate the device.

The current prototype operates on a 9 – 12 V battery and can be triggered by a smartphone or tablet app, thereby allowing it to be *potentially used for stimulation treatment at home in the future*.

**Flexibility of TRPMS applications:** Earlier studies involving repeated stimulation of the left inferior frontal gyrus pars triangularis (IFG) has shown that TRPMS stimulation of this part of Broca's area during encoding of words facilitates word memory. In contrast, chronic repeated stimulation of this area at rest in the absence of word memorization disrupts it. A preliminary open label study done in one chronic ischemic stroke (CIS) patient prior to the start of an ongoing randomized double blind sham treatment-controlled trial, has revealed the following restorative changes: after 2 two-week sessions of treatment, movement-related fMRI showed increasing levels

of neural activation of the stimulated intact cortex surrounding the lesion. Marked quantitative improvements were seen in grip strength, lower extremity motor function, and sensation measures on the affected side, as well as gait speed. These changes persisted at the 3-month follow-up time point after two other two-week treatment sessions. Other unpublished studies in healthy adults have shown modulatory effects on perception of body ownership, numerical ability, motor skill learning and functional connectivity of cortical areas.

- ***Therapeutic effects of multifocal TRPMS are currently being studied in pilot clinical trials on developmental stuttering, CIS, and type 1 myotonic dystrophy at our institution.***

Safety profile of TRPMS: Repeated cerebral cortical stimulation with this device is well tolerated with no reported serious adverse events in more than 200 adult human subjects, including patients with chronic ischemic stroke, amyotrophic lateral sclerosis, type 1 myotonic dystrophy, and developmental stuttering in our institution. Electroencephalographic recordings in 45 subjects have demonstrated that repeated TRPMS stimulation does not induce seizures or epileptiform changes.

- ***TRPMS has been determined to be a Non-Significant Risk device by the Food and Drug Administration.*** Please see attachments under appendix for this proposal.

Regions of Interest (ROI) from the literature: Earlier neuroimaging studies have identified brain regions directly involved in initiating or continuing voiding in **healthy** individuals. These regions include: Precentral Gyrus, Supplementary Motor Area, Dorsolateral Prefrontal Lobe, Inferior Frontal Gyrus (IFG), Cingulate Gyrus, Insula, Hypothalamus, PAG, and Pons (PMC). Although, PAG and PMC are the more apparent regions involved in initiation of voiding and could serve as potential targets for intervention, they are deep and inaccessible with our current technological modalities. Besides, these regions are responsible for other core vital functions such as regulating circulation and breathing wherein modulation would not be safe.

- On the other hand, ***we propose that if we shift our focus to modulate areas of the brain that are more cortically accessible and amendable to modulation, such as areas responsible for urethral sphincter relaxation, we may indirectly improve voiding.*** Table 1 summarizes the currently available cortical brain regions involved in voiding as potential ROIs in healthy, MS and non-neurogenic VD.

MNI	BA	HA	Area	Neuroimaging	Task	Reference
Healthy						
52, 24, 12	45/44	Right	IFG	PET	Voiding	Blok 1998 
63, 18, 18	44/45	Right	IFG	fMRI	Initiation of voiding	Mehnert 2015 
40, 35, 6	46	Right	IFG	fMRI	Initiation of voiding	[name] 2014
8, -8, 62	6	Right	Medial frontal gyrus	fMRI	PF contraction	Zhang 2005 
6, -18, 57 3, -18, 57	6	Right	Medial frontal gyrus	PET	PF contraction	Kuhtz-buschbeck 2005 
2, 2, 62	6	Right	Superior frontal gyrus	fMRI	PF contraction	Kuhtz-buschbeck 2011 
48, 4, 10	6	Right	IFG	PET	Voiding (urethral)	Nour 2000 
-44, 1, 28	6	Left	Precentral gyrus	fMRI	Initiation of voiding	[name] 2014
2, -32, 66	4	Right	Superiomedial precentral	PET	Voiding	Blok/Holstege 1997 
-6, -26, 74	4	Left	Superiomedial precentral	PET	Voiding	Blok/Holstege 1997 
Non-neurogenic voiding dysfunction						
54, -4, 6	6	Right	Precentral	fMRI	Urethra	Fowler 2010 
Neurogenic voiding dysfunction (MS)						
-39, 34, 5	45	Left	IFG	fMRI	Initiation of voiding	[name] 2017
38, 33, 6	45	Right	IFG	fMRI	Voiding	[name] 2017

[figure not shown]
Table 1: MNI: Montreal Neurological Institute coordinates; BA: Brodmann Areas; HA: Hemisphere; PF: Pelvic Floor

In a small group of women with urinary retention, due to urethral sphincter dysfunction, *peripheral nerve* neuromodulation modified the activity of the right postcentral gyrus, precentral/temporal, and inferior temporal regions. fMRI studies report that medial prefrontal cortex and supplementary motor areas are the main cortical regions involved in pelvic floor contraction, and could be used to phenotype responders versus non-responders to biofeedback assisted pelvic floor physical therapy in overactive bladder patients.

- Aims 1 and 2 of this proposal characterize specific brain regions that are activated during voiding in MS and these regions will be added to the current data (table 1) to individualize the targets used in aim 3 for multi-site transcranial modulation.

### 3. APPROACH

#### Preliminary Data over the past four years

[figure not shown]
a three-dimensional augmented reality (AR) device in HC during repetitive voiding. The network under investigation was found to consist of two large sub-networks, one in the frontal lobe and one that connected sensory regions with deeper brain structures, including the PMC. This data will serve as our HC for this proposal.

**MS patients:** We have evaluated twenty-seven MS patients with neurogenic lower urinary tract dysfunction using our established fMRI/UDS platform. Our analyses described, for the first time, brain regions activated at initiation of voiding in female

Figure 4. BOLD signals at initiation of voiding. A, HCs B, MS showing higher signals in regions with warmer colors. C, subtraction image between MS and HCs.

**Healthy Controls (HC):** Our established fMRI/UDS platform demonstrated activation of brain regions of cerebellum, thalamus, caudate, lentiform nucleus, supplementary motor area, postcentral gyrus, left superior frontal gyrus, anterior and posterior cingulate gyrus and insula, as well as other brain structures such as the pons at the time of “initiation of voiding” HC, figure 3. We also have established an algorithm visualization and evaluation of neuroimaging data

Figure 3. Average fMRI activation maps with concurrent UDS tracings. Asterisk denote “initiation of voiding” in the event-related analysis of the fMRI data in HC.

[figure not shown]

MS patients (Figure 4).

**MS patients with DSD:** Our data on a subgroup analysis of MS patients with DSD (n=4), showed statistically significant greater activation in the right middle frontal gyrus, right medial frontal gyrus, right cingulate gyrus, right caudate nucleus, and brainstem at “initiation of voiding”.

**Changes in brain following intradetrusor injection of OnabotulinumtoxinA (IDBTX-A):** fMRI/UDS results from our recent study examining the impact of IDBTX-A in MS with urinary urgency (N=12) demonstrated that activation increased in specific brain regions associated with the sensation and process of urinary urgency six weeks post therapy (Figure 5). This is the first study of its kind to evaluate the possible sensory effects of IDBTX-A in humans. These preliminary results have been submitted to the 2018 national Urology and Neurology meeting.

Figure 5. A. subtraction BOLD activation maps of post minus pre IDBTX-A for the ROIs in sagittal (1 and 2) and horizontal (w and 4) images. 1) Right Cingulate 2) Pons 3) Insula 4) Right Prefrontal Cortex; B. ROI coordinates using MNI and RPI coordinates, and the p values.

## OBJECTIVES/ SPECIFIC AIMS/ HYPOTHESES

**A priori selected grey matter Regions of Interest for aim 1:** Based on our preliminary data and the summary of literature outlined in table 1, we propose the following *a priori* selected ROIs for the **cortical and deep grey matter and nuclei for aim 1**: Inferior frontal and precentral gyrus, thalamus, PAG, and pons. **A priori selected white matter tracts (WMT) for aim 2:** Since MS lesions affect the white matter mainly, it is prudent to evaluate the WMT involved in bladder function in this patient population. Two WMTs are particularly important in proper function of the bladder: Anterior thalamic radiation (ATR) and Superior longitudinal fasciculus (SLF).

Clinical and UDS data will be used to categorize female MS patients with stable disease into two groups. The standardization of terminology by the International Continence Society does not provide clear definition for VD, however we propose the following based on expert opinion. Group 1: MS patients with VD (patients who perform self-catheterization or have a postvoid residual of urine  $\geq 20\%$  Maximum Cystometric Capacity); and Group 2: MS patients without VD (patients who void spontaneously and their postvoid residual of urine  $< 40\%$  Maximum Cystometric Capacity). Patients in Group 1 will be further subdivided into patients with DSD (Group 1a) versus without DSD (Group 1b). DSD is defined as increased EMG activity  $\geq 20\%$  during detrusor contraction (voiding) in the absence of valsalva maneuvers on UDS.

We **hypothesize** that female MS patients with VD have a distinct pattern of brain activation and connectivity at “initiation of voiding” and targeted cortical modulation may be feasible and lead to improved voiding.

**Specific Aim 1: Activation patterns of the grey matter ROIs are different among female MS subjects with VD, specifically those with DSD.** We will determine the distinct activation patterns by:

- Assessing Blood Oxygen Level Dependent (BOLD) signal and functional connectivity (FC) patterns in the ROI's at “initiation of voiding” in Groups 1a, 1b, and 2.
- Comparing BOLD signals and FC patterns in Group 1 versus 2, and specifically Group 1a versus 1b.

**Specific Aim 2: Damage to preselected WMT in female MS patients provides an independent predictive measure for VD.** We will use diffusion tensor imaging and our established algorithm of measurement to:

- Measure fractional anisotropy (FA) and mean diffusivity (MD) of the ATR and SLF in Groups 1a, 1b, and 2.
- Assess whether damage to SLF or ATR are associated with voiding dysfunction in our patient population.

**Specific Aim 3: Targeted cortical stimulation in Group 1 causes changes in ROI (identified during specific aim1) that better recapitulate the activation patterns in group 2 or HCs by:**

- Assessing BOLD and FC activation in the ROIs following individualized TRPMS in patients in Group 1.
- Evaluating voiding improvement via UDS and validated questionnaires following TRPMS.

- c) Identifying baseline clinical/UDS or neuroimaging factors that could predict response to TRPMS.
- d) Evaluating EMG changes in the pelvic floor following TRPMS.

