## EXPERIMENTAL PLAN AND FEASIBILITY

We have completed and recently published a well-powered study, on twenty-seven female MS patients, that evaluated brain response to bladder filling during the bladder *storage phase*. Aims 1 and 2 are retrospective analysis of the *voiding phase* from our extensive and meticulously collected neuroimaging raw data available to us from our prior completed cohort. Aim 3 is a small, pilot feasibility study (n=8).

**Study duration:** Based on our experience, we anticipate that one year will allow appropriate time for data analysis for Aims 1 and 2. An additional (concurrent) 1-2 years will allow for appropriate patient recruitment, performance of the protocols, and data evaluation for Aim 3.

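### Two BOLD results in Aim 1, left inferior frontal activation in MS patients and the DSD brainstem/pons contrast, appear to have been seen already in the cohort being re-analysed, so a p-value for them is not an independent test

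*Combined protocol and SAP*

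**What the plan says.** **Choice of regions.** Under Objectives/Specific Aims/Hypotheses, the Aim 1 regions are "Inferior frontal and precentral gyrus, thalamus, PAG, and pons", selected "Based on our preliminary data and the summary of literature outlined in table 1". Aim 1 hypothesises different activation in patients with voiding dysfunction, in particular those with DSD, and compares Group 1 with 2 and Group 1a with 1b.

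**Results in hand.** Under Preliminary Data: "We have evaluated twenty-seven MS patients with neurogenic lower urinary tract dysfunction using our established fMRI/UDS platform". It continues: "Our analyses described, for the first time, brain regions activated at initiation of voiding in female" MS patients (Figure 4, reference 17). For DSD: "Our data on a subgroup analysis of MS patients with DSD (n=4), showed statistically significant greater activation" in the right middle frontal, right medial frontal and right cingulate gyri, the right caudate and the brainstem, also at initiation of voiding and also from reference 17. Both rows of Table 1 under "Neurogenic voiding dysfunction (MS") come from reference 17: left IFG at initiation of voiding and right IFG at voiding.

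**Data for Aim 1.** Experimental Plan and Feasibility describes the 27-patient reference 17 study, then says that Aims 1 and 2 retrospectively analyse the voiding phase in "meticulously collected neuroimaging raw data available to us from our prior completed cohort". The Power Analysis says that scanning for these aims is finished and analysis awaits funding.

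**Endpoints.** Primary endpoint (a) is BOLD intensity and functional connectivity in the preselected regions at initiation of voiding. Secondary endpoint (c) is BOLD and connectivity with versus without DSD.

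**The concern.** Preselecting regions protects against chance findings only if the selection did not use the data later tested. Here part of the selection, and probably the DSD hypothesis, follows voiding-phase results from what appear to be the same patients. A significant left IFG activation or DSD difference in pons could then be read as a prespecified hypothesis borne out, when it repeats an observation already made. The p-value would be too small, and the effect size would probably be overestimated, most of all with four DSD patients. The plan provides no split sample, independent sample or exploratory label for these results. Its limitations section also credits preselection with better specificity, a benefit that is lost wherever the selection used the same data.

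**Working it through.** **1. Is it the same cohort?** The plan's group size is 12 inflated for 10% movement exclusions: 12 / 0.9 = 13.3, or 12 × 1.1 = 13.2. Rounded to the nearest integer this is 13 per group, 26 in total, as stated (rounding up gives 14 and 28). The figure of 12 cannot be derived, because no effect size or SD is given. The 26 fit within the 27 patients already scanned, and the reference to a prior completed cohort directly follows the account of those 27. Identity is a strong inference; no patient list confirms it.

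**2. Which regions depend on this cohort?**

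| Aim 1 region | MS source (reference 17) | Support outside the MS cohort |
|---|---|---|
| Left IFG | Table 1 | None in Table 1 |
| Right IFG | Table 1 | Four healthy-subject rows in Table 1 |
| Precentral gyrus | None in Table 1 | Healthy and non-neurogenic rows in Table 1 |
| Thalamus | None stated | Team's healthy controls |
| PAG | None stated | Healthy-subject literature in the Innovation section |
| Pons | DSD result, as brainstem | Healthy-subject literature and the team's healthy controls |

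For activation itself, only left IFG rests on the MS cohort alone. For the DSD contrast, the earlier result overlaps the Aim 1 regions only through brainstem/pons.

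**3. Re-testing a known DSD result.** Inputs: 4 DSD patients (Preliminary Data), 13 per group (Power Analysis), 27 in the cohort. Assumptions: Group 1b = 13 − 4 = 9; one of the 27 unused in the re-test (27 − 26); the earlier comparison was DSD versus the other 23 patients. Independent standard normal data were simulated with no true difference, using two-sided t-tests at 0.05.

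- 1a versus 1b, unconditionally: 5.0%.
- 1a versus 1b, given that DSD versus the rest was already significant: 52%.
- If instead the region was the strongest of 5, 10, 20 or 50 on DSD versus the rest: 18%, 30%, 41% or 63%.
- If the earlier comparison was exactly 1a versus 1b with the same method, the re-test returns the earlier answer and adds nothing.

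**4. Size of effect.** With 4 versus 9, 80% power needs d = 1.85. If the true difference were d = 0.8, significant results in that direction would average about d = 1.8.

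**5. Group 1 versus 2.** Selecting a region on pooled MS activation and then testing Group 1 versus 2 gives about 4.5% to 5.5%, essentially nominal. There is one spill-over. In a region where the DSD result is already known to be significant, the simulation gives about 12% for Group 1 versus 2, because the DSD patients sit inside Group 1. This concerns brainstem/pons only.

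**The case against.** The plan discloses much of this. It says that the regions use preliminary data, that Aims 1 and 2 are retrospective and that scanning is complete, and it never uses the word confirmatory. Four of the five areas reported for the DSD patients are not Aim 1 regions, which suggests that the DSD result did not drive the list. The earlier comparator is not stated, and pons has support elsewhere. These points stand. They narrow the concern, but they do not tell a reader that these two particular results had already been seen.

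Stronger readings are tempting, and the documents do not support them:

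- *That Aim 1 as a whole is circular.* Most regions have healthy-subject support. The earlier MS maps are described as MS activation and MS minus healthy controls, not Group 1 versus 2. No earlier MS connectivity result for voiding is reported, so the connectivity half of the primary endpoint is untouched.
- *That an inflated pons result would steer Aim 3 stimulation.* Aim 3 uses superficial cortical targets, and the Innovation section calls the pontine micturition centre and PAG deep and inaccessible.
- *That the Aim 3 baseline scans provide a replication.* There are eight patients, all Group 1. Even a 4 versus 4 DSD split needs d = 2.38, and it is unclear whether some belong to the earlier cohort.

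**Conclusion.** The concern holds for two BOLD results: left IFG activation in MS patients, and the 1a versus 1b contrast in brainstem/pons. For these, a p-value from the same data is not an independent test. For the DSD contrast the illustrative false-positive rate under a null is roughly 50% rather than 5%. That figure depends on the assumed 4, 9 and 13 split and on DSD versus the rest as the earlier comparison, neither of which the documents give. The whole point also rests on the inferred identity of the cohort. That the DSD hypothesis grew out of the four-patient result is likely but not stated.

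The Group 1 versus 2 contrast (apart from the spill-over in pons), functional connectivity, and activation in right IFG, precentral gyrus, thalamus, PAG and pons are not materially affected.

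Separately, the accounts of reference 17 conflict. Experimental Plan and Feasibility calls it a storage-phase study and the Power Analysis says that analysis is pending, yet Table 1 and the Preliminary Data credit it with voiding results.

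**What to change.** 1. In Objectives/Specific Aims/Hypotheses and in Endpoints, state that MS left IFG activation and the DSD brainstem difference at initiation of voiding have already been observed in this cohort. Label both exploratory, and report estimates with confidence intervals and no confirmatory p-value. Give the comparator of the earlier DSD analysis.
2. Define the Aim 1 IFG mask anatomically from an atlas, not around the two MS coordinates in Table 1. The regions are named as anatomical structures, so this may only make the existing intention explicit.
3. Reconcile the storage-phase description of reference 17 and the statement that analysis is pending with the voiding results credited to that reference. State how far the Aim 1 patients overlap with the 27.
4. If Aim 3 baseline scans are shown alongside, present them only as a small descriptive check of MS activation, and only for patients outside the earlier cohort.

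The cost is wording and a mask definition, with no new data. The downside is a more modest label on these two results.
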